8.6.2.3. Urine Drug Screen

A urine drug screen will be performed at the time points specified in Table 1 and Table 2 of the study protocol. The urine drug screen detects the presence of drugs of abuse, including amphetamine, barbiturates, benzodiazepines, cocaine, opiates, and tetrahydrocannabinol.

Any findings will be listed.

8.6.2.4. Prolactin

Blood samples will be obtained for prolactin test at the time points specified in Table 1 and Table 2 of the study protocol. The test results will remain blinded to the sponsor until the database lock for efficacy analysis.

Note: in order to maintain the blind, prolactin level results, other the ones obtained before the first IMP administration per protocol, will not be available for review by the sponsor or the sites until visit 13 (8 weeks into Period 2).

The test results will be presented as described for all the clinical laboratory test results outlined in Section 8.6 above. In addition, summaries of potentially clinically significant abnormal values from baseline - from normal to 2x ULN and 5x ULN - will be presented.

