8.4.2.3. Prolactin

Blood samples will be obtained for prolactin test at the time points specified in [Table 1](#) and [Table 2](#) (at screening [prior to intake of oral olanzapine, where relevant], baseline [visit 2; week 0 (prior to IMP administration)], visit 11 [week 8 (prior to IMP administration)], visit 14 [week 20 (prior to IMP administration)], and at the EOT visit). As prolactin levels are highly affected by olanzapine and reach steady state approximately 8 weeks after treatment initiation ([Yang et al 2018](#)), in order to maintain the blind, prolactin level results obtained after first IMP administration and before visit 13 (8 weeks into Period 2) will not be available for review by the sponsor or the sites until Period 1 database lock. The IDMC will review the unblinded data periodically.

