This Statistical Analysis Plan (SAP) describes the planned analysis and reporting for Teva Branded Pharmaceutical Products R&D, study TV44749-CNS-30096, (A Multinational, Multicenter, Randomized, Double-Blind, Parallel-Group, Placebo-Controlled Study with an Open-Label, Long-Term Safety Phase to Evaluate the Efficacy, Safety, and Tolerability of Olanzapine for Extended-Release Injectable Suspension (TV-44749) for Subcutaneous Use as Treatment of Adult Patients with Schizophrenia), and was written in accordance with standard operating procedure (SOP) GSD-SOP-702 (Statistical Analysis Plan).

The reader of this SAP is encouraged to read the study protocol with amendment 01 (approved on February 15, 2024) for details on the conduct of this study, the operational aspects of clinical assessments, and the timing for completing the participation of a patient in this study.

The SAP is intended to be in agreement with the protocol, especially with regards to the primary and all secondary endpoints and their respective analyses. However, this SAP may contain more details regarding these particular points of interest, or other types of analyses (e.g., other endpoints). When differences exist in descriptions or explanations provided in the study protocol and this SAP, the SAP prevails; the differences will be explained in the Clinical Study Report.

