In addition, any use of prohibited antipsychotics after early termination is not considered an ICE. Prior antipsychotic medications without a defined end-date are not deemed as ICE of "prohibited concomitant antipsychotic medication" since these cases occur before randomization and initiation of treatment.

Table 1: Classification of Intercurrent Events

Intercurrent Event	Strategy	Handling of Intercurrent Events

 • Early discontinuation of treatment due to: 
 ◦ lack of efficacy ◦ disease progression • Prohibited antipsychotic (with the exception above) 	Hypothetical	Measurements after ICE will be removed and replaced with imputed data using reference-based (CIR) imputation (assuming MNAR)

 • Early discontinuation of treatment due to other reasons (including due to adverse event) 	Hypothetical	Measurements after ICE will be removed and replaced with imputed data based on randomized treatment group (assuming MAR)

 • Allowed concomitant medications • Adverse event that did not lead to treatment discontinuation • Use of prohibited medications that are not antipsychotic • Short term use of prohibited antipsychotic (see meeting the definition above) • Injection site reaction • Out of window safety assessments 	Treatment policy	Measurements after ICE will be included in the primary analysis

ICE=intercurrent event; MAR=missing at random; MNAR=missing not at random; CIR = copy increments in reference

Any data collected after the intercurrent event (ICE) of taking prohibited antipsychotic medications (except as described above) or withdrawal from randomized treatment due to insufficient clinical response (i.e., lack of efficacy) will be treated in the analysis as MNAR. An ICE of early discontinuation for other reasons will be treated in the analysis as if the patient fully complied and completed the study (i.e., assuming missing at random [MAR]); see Table 1 for further details on the classification and handling of ICEs. This complies with the hypothetical approach.

For ICEs that were not foreseen at the time of writing the protocol and that require the use of the hypothetical strategy, classification as MAR/MNAR and revisiting this classification will be done in a blinded manner on a case-by-case basis prior to database lock for efficacy and will be

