2.2.2. Discontinuation of the Placebo Treatment Group

After approximately 440 patients complete the week 8 visit, depending on the need for additional data on exposure or safety, the placebo treatment group may be discontinued and additional patients may be randomized to the study (ie, to Period 1) to the TV-44749 treatment groups only. Patients randomized to the study from that time point will not be included in the primary efficacy analyses, as there will be no concurrent placebo group. The sponsor will notify the sites and the IDMC once the placebo treatment group is discontinued, and new patients from that time point will sign an updated ICF reflecting the actual available treatment groups.

Once all patients who were still ongoing in Period 1 at the time of the placebo group discontinuation will either complete or early terminate from Period 1, and are randomized into

Period 2 (if applicable), randomization into Period 2 will no longer be performed, as at that point, all patients in Period 1 will be assigned to TV-44749 treatment groups and will continue their treatment assignment in Period 2 as well.

Period 1 will remain blinded until database lock for efficacy, including for patients randomized after the discontinuation of the placebo treatment group as long as they are still in Period 1. After the data are locked for efficacy analyses, the study may continue in an unblinded manner.

Period 1 efficacy data collected from patients randomized after discontinuation of the placebo treatment group will not be included in the primary analysis. Therefore, revealing of Period 1 treatment assignment (ie, since patients will be continuing their treatment assignment in Period 2) for patients who were randomized to the study after discontinuation of the placebo treatment group will not be considered unblinding.

Additional details regarding maintenance of randomization and blinding are described in Section 6.10 of the study protocol.

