17.2. Conditional Power Evaluation for IDMC

Initially this study's accrual period was expected to be 19 months, however at the time of writing this SAP, the revised expected accrual period is 11 months. As stated in the protocol, a conditional power calculation was planned to be provided to the IDMC when 50% of patients completed Visit 11 as a means of evaluating whether termination of the study was warranted if safety concerns arose. However, since the accrual rate is much higher than anticipated, it is now expected that at the time of reaching 50% accrual, the additional information gained for the remainder of the study would be limited. In fact, at the next planned IDMC meeting, there was only approximately 10% of person-time remaining before the end of accrual in Period 1 (i.e., the time at which efficacy will be evaluated).

Therefore, given these calculations that support an unexpected fast accrual rate, it has been decided that the conditional power analysis will not be conducted as planned. This decision was vetted with the IDMC and the final arbitration will be documented in the IDMC meeting minutes.

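### The SAP prolactin note still uses the visit-13 release point, while the protocol withholds the same results from sponsor and sites until Period 1 database lock

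*SAP*

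**What the plan says.** SAP section 8.6.2.4 has two statements on access to prolactin.

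- Its first paragraph covers the sponsor only: "The test results will remain blinded to the sponsor until the database lock for efficacy analysis".
- The note that follows exempts results from before the first injection and says that the others "will not be available for review by the sponsor or the sites until visit 13 (8 weeks into Period 2".

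Protocol section 8.4.2.3, with the same rule in section 6.10.2, covers results obtained once the first injection has been given. Its release rule reads: "before visit 13 (8 weeks into Period 2) will not be available for review by the sponsor or the sites until Period 1 database lock". Olanzapine's strong effect on prolactin is the reason given. The IDMC may see unblinded data.

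On precedence, the SAP Introduction says: "When differences exist in descriptions or explanations provided in the study protocol and this SAP, the SAP prevails". Protocol sections 10 and 10.13 say the same. SAP section 2.2.2, on blinding, adds: "Additional details regarding maintenance of randomization and blinding are described in Section 6.10 of the study protocol". Protocol section 6.10 contains the database-lock rule.

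**The concern.** Two current documents give different release points for the same laboratory results, and the document with the earlier release point claims precedence. Administrative Letter 01 (27 November 2022) explains the origin: it replaced release at visit 13 with release at Period 1 lock. The current protocol has the new rule and the current SAP note has the old one. SAP section 17, which lists changes from the protocol, does not mention prolactin, so the note looks like leftover text and not a decision.

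What is at stake is the Period 1 blind. Protocol sections 4.1 and 6.9 keep Period 1 blinded to sponsor, site staff and participants until lock. Sites learn each patient's Period 2 dose after week 8, and patients on active drug keep their Period 1 dose. The main fact still hidden is then whether a patient had active drug or placebo in Period 1, and week-8 prolactin bears on exactly that. A site following the SAP note could have this information before lock, possibly while its raters are still scoring other Period 1 patients on the PANSS.

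**Working it through.** **Setting the rules side by side**

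| Party | Protocol 6.10.2 and 8.4.2.3 | SAP 8.6.2.4, first paragraph | SAP 8.6.2.4, note |
|---|---|---|---|
| Sponsor | Period 1 lock | Efficacy lock | Visit 13 |
| Sites | Period 1 lock | Not mentioned | Visit 13 |

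For the sponsor, the SAP disagrees with itself, and a clause ranking SAP over protocol cannot settle that. For the sites, the note is the only rule in that section and it disagrees with the protocol.

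**How many patients would pass visit 13 before lock**

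The documents give no figure to reproduce, so this is an illustration.

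Inputs:
- Accrual: SAP section 17.2 states that "the revised expected accrual period is 11 months". In weeks, A = 11 × 365.25 / 12 / 7 = 47.8.
- Visit 13 is at week 16 (Protocol, Appendix B).
- Completion of Period 1: 440 completers of 640 randomized (SAP section 2.5), or 440/640 = 0.6875.
- Assumptions: uniform accrual, and lock L weeks after the last randomization. L = 8 is when the last patient reaches week 8.

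Share of Period 2 entrants past visit 13 at lock = (A − (16 − L)) / A, capped at 1. Multiplying by 0.6875 gives the share of all randomized, because patients who leave in Period 1 never reach visit 13.

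- L = 8: (47.8 − 8) / 47.8 = 0.83; × 0.6875 = 0.57
- L = 11: (47.8 − 5) / 47.8 = 0.90; × 0.6875 = 0.62
- L = 16: 1.00; × 0.6875 = 0.69

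When enrolment closes: (47.8 − 16) / 47.8 = 0.67 of those continuing; × 0.6875 = 0.46 of all randomized.

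With accrual varied from 9 to 19 months at L = 8, the share of all randomized runs from 55% to 62%.

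**What prolactin would add to what sites already know**

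Under 1:1:1:1 allocation with equal completion, a given Period 2 dose group contains its own Period 1 arm plus one third of the placebo arm. The chance that a patient had the same dose in Period 1 is 1 / (1 + 1/3) = 75% before any prolactin result.

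The documents give no sensitivity, specificity or cut-off. If sensitivity and specificity both equal s (an assumption), then:

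- a call of placebo is right with probability 0.25s / (0.25s + 0.75(1 − s));
- a call of active is right with probability 0.75s / (0.75s + 0.25(1 − s)).

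| s | Placebo call right | Active call right |
|---|---|---|
| 0.70 | 44% | 88% |
| 0.80 | 57% | 92% |
| 0.90 | 75% | 96% |
| 0.95 | 86% | 98% |

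The gain therefore runs from modest to substantial, depending on an accuracy that the documents do not state.

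**The case against.** **The SAP came too late to matter.** The original SAP is dated 23 October 2023 and the amendment 17 April 2024, whereas the lock rule went to investigators in November 2022. By 29 January 2024, 675 patients had been randomized against about 640 planned. The amendment came 79 days (11.3 weeks) after that date. If accrual had ended by then, which is an assumption, every scheduled week-8 rating was finished before the amended text existed. The wording of the October 2023 SAP is not available. This stands as a limit on size: the percentages count patients as if the note had applied throughout accrual. It does not remove the conflict before lock, because SAP section 2.6.2 requires SAP amendments to be approved before the first lock.

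**Sites work from the protocol, and the SAP defers to it.** The protocol's precedence clause sits in its statistics section, and SAP section 2.2.2 points to protocol section 6.10. Sites may well follow the protocol in practice. A general cross-reference, however, does not clearly override a specific rule about sites in a document that says it prevails.

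**The sponsor is still blinded.** A reader might infer that the note unblinds the team that classifies intercurrent events, for which SAP section 1.2.1 says "classification as MAR/MNAR and revisiting this classification will be done in a blinded manner on a case-by-case basis prior to database lock". The documents do not support that. The sentence above the note keeps the sponsor blinded until efficacy lock, and the note's wording can be read as the earliest possible date, not an instruction to release. What remains is an internal contradiction to remove.

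**The arm is not shown to be inferable.** A reader might also conclude that most patients' Period 1 arm could be worked out before lock. Passing visit 13 is not the same as being identified. Prolactin accuracy is not given, and the revealed Period 2 dose alone already supports a correct guess about 75% of the time.

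**Conclusion.** The SAP note is wrong against the current protocol and, for the sponsor, against the SAP's own preceding sentence. It should be corrected. The practical exposure is at the sites, which under the note could see week-8 prolactin before lock and possibly while other Period 1 patients are still being rated.

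On size, about 83% of Period 2 entrants, or 57% of all randomized, would pass visit 13 before lock. This rests on uniform 11-month accrual, lock 8 weeks after the last randomization, and 440/640 completion. A later lock raises the arithmetic. The late date of the SAP makes it an upper-range illustration of what the note could have exposed, and it is not an estimate of unblinding.

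Two further readings should be avoided. A patient's own week-8 ratings cannot be biased, because visit 13 falls 8 weeks after them. Nor does the protocol withhold every post-dose prolactin result until lock; it withholds those obtained before visit 13. No estimate, power, alpha or sample size figure changes.

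**What to change.** Replace the note in SAP section 8.6.2.4 with the protocol rule: prolactin results obtained after the first injection and before visit 13 stay unavailable to sponsor and sites until Period 1 database lock, with the IDMC excepted. It would help to say that this includes end-of-treatment samples from patients who leave before visit 13, since the present note gives them no clear release point. Also document, for example in the clinical study report, whether any such result was released to a site or the sponsor before lock. The cost is one sentence in the SAP and a check of laboratory release records; no analysis changes.

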8.7. Physical Examinations

Physical examinations, including height (to be obtained at the screening visit only) and weight, will be performed at the time points detailed in Table 1 and Table 2 of the study protocol. Full physical examination will be conducted at the screening visit and unscheduled visits only; the rest of the visits will include an abbreviated physical examination (including weight). The full physical examination will consist of examining the following body systems: cardiovascular, respiratory, abdominal, skin, neurological, and musculoskeletal systems. The physical examination will also include examination of general appearance, including head, eyes, ears, nose, and throat; chest; abdomen; skin; lymph nodes; and extremities. An abbreviated physical examination (general appearance, head, eyes, ears, nose, throat, lung, heart, skin, and extremities) will be conducted at the other time points and will include a brief neurological examination that includes examination of a subset of cranial nerves controlling vision and motor examination of a subset of larger muscle groups, including an assessment of muscle tone, reflexes, gait, and involuntary movements.

Any new physical examination finding that is judged by the investigator as clinically significant (except at the screening visit) will be considered an adverse event, recorded on the CRF, and monitored as described in Section 8.5 of the study protocol.

Descriptive statistics for weight will be provided. The values and percent changes from baseline to each visit in period 1 and for the integrated study periods will be presented for the safety analysis set. Weight shifts from reference to each visit by treatment group will be presented, where the reference is the screening measurement, using the following limits: ‘<0’, ‘(0-7%]’, ‘(7-10%]’ and ‘≥10%’

All the data will be listed. Boxplots for weight will be presented by visit and treatment group.

In addition, BMI values and changes from baseline to each visit (which weight was collected) in period 1 and for the integrated study periods will be presented for the safety analysis set.

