3.3. Safety Analysis Set

The safety analysis set for Period 1 will include all randomized patients who received at least 1 dose of TV-44749 or placebo. The safety analysis set for Period 2 will include all randomized patients to Period 2 who received at least 1 dose of TV-44749. For the integrated study periods summary tables (see Section [8](#)) the safety analysis set will include all patients in the safety analysis set of period 1 that received 1 of the 3 TV-44749 treatments groups, or all patients that meet the definition of the safety analysis set of Period 2.

In each of the safety analysis sets, treatment will be assigned based on the initial treatment patients actually received in the corresponding period, regardless of the treatment to which they were randomized, and regardless of dose adjustments, unless otherwise specified. For the integrated periods summary tables, patients randomized in Period 1 to 1 of the 3 TV-44749 groups will be counted according to the initial dose they actually received in Period 1. Patients that were randomized to Placebo in Period 1 will be counted according to the initial dose of TV-44749 they actually received after the re-randomization of those patients to the 1 of the 3 TV-44749 treatment groups in Period 2, regardless of dose adjustment that may occur during Period 2.

In cases of dosing error, a decision of what is the treatment assignment for these patients will be made in a blinded manner prior to unblinding of Period 1, as applicable. The decision will be made during the statistical data review meeting and will be documented in the statistical data review document.

For IDMC monitoring during the study, the safety analysis set will use the treatment based on the randomization assignment in the opening of each period.

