4. GENERAL ISSUES FOR DATA ANALYSIS

4.1. General

Descriptive statistics for continuous variables include n, mean, standard deviation (SD), median, minimum, and maximum. When appropriate, least squares means and standard errors (SE) are presented. Descriptive statistics for categorical variables include patient counts and percentages. Missing categories will be displayed as appropriate.

For the CSR and IDMC closed reports, summary tables by treatment groups will have 2 versions – (a) summary tables for Period 1; (b) summary tables for the integrated periods including patients from both Periods (Period 1 & Period 2), unless otherwise specified. For IDMC open reports, a summary tables for Period 1 and Period 2 will be generated and will only be presented overall (total).

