4.2. Specification of Baseline Values

For Period 1, the baseline value for a patient is the last observed data that was collected for this patient prior to the first IMP dose administration, unless otherwise noted.

For Period 2, the baseline value for a patient is the last observed data that was collected for a patient prior to the third IMP administration (i.e., first administration in period 2, at visit 11, week 8), unless otherwise specified (see procedures and assessments which may be performed after the re-randomization to Period 2 at visit 11 in Section 6.9.1 in the study protocol).

For the integrated periods to be presented in the CSR and during the IDMC closed (in an unblinded manner) and open (in a blinded manner) sessions, the baseline values of patients initially randomized in Period 1 to TV-44749 groups will be defined as the last observed data that was collected prior to the first TV-44749 dose administration. For patients that were assigned to placebo group in Period 1, the baseline value is the baseline value for Period 2 (see above paragraph).

It should be noted that the baseline values of placebo patients will differ between tables presented in the integrated periods summaries and those presented in Period 1 summaries.

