8. SAFETY ANALYSIS

8.1. General

Safety analyses will follow the safety estimand approach using the safety analysis sets.

Safety will be assessed by qualified study personnel by evaluating reported adverse events (including serious adverse events, extrapyramidal symptoms, injection pain, injection site findings and Injection Site Reactions [ISRs]), vital signs (blood pressure, pulse and orthostatic changes, and temperature), body weight and BMI, laboratory tests, ECG, concomitant medication use, time to all-cause discontinuation, all-cause discontinuation rates and discontinuation rates due to adverse events (tolerability), time to all discontinuation by reason, and safety rating scales (including Abnormal Involuntary Movement Scale [AIMS], Barnes Akathisia Rating Scale [BARS], Simpson-Angus Scale [SAS], C-SSRS, and CDSS).

Safety assessments and time points are provided in Table 1 (for Period 1) and Table 2 (for Period 2) of the study protocol.

The safety analysis will be performed separately for Period 1 and for the integrated study periods.

The safety analysis for Period 1 will be performed by treatment group and overall (total).

The safety analysis for the integrated study periods that will be presented in the CSR and in the IDMC closed reviews, will be performed by treatment group. Specifically, for IDMC closed reviews, patients rolling over from Placebo group will be distinguished from patients who continued their active treatment assignment from Period 1. Data from Period 1 for placebo patients will not be included in the integrated summaries.

For the open sessions of the IDMC reviews, data from Period 1 and from Period 2 will be presented separately. Summary tables will be generated for each period and will only be presented as a single total column.

For the following safety variables: Adverse events, Clinical laboratory results, ECG, weight and BMI and Vital signs, a separate safety summary will be presented for the 'While on Treatment' period, defined as the period between the first IMP administration visit until and including the End of Treatment visit (including the Early Termination visit if conducted during this period). In addition a separate safety summary table and listing will be presented for the Follow-Up period, defined as the period after the End of Treatment/Early Termination visit until the end of the study.

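### The weight-shift table in SAP 8.7 is referenced to screening, so its integrated version counts former-placebo patients' weight change on placebo under a TV-44749 dose

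*SAP*

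**What the plan says.** SAP 8.7 plans two weight summaries with different starting points. For percent change: "The values and percent changes from baseline to each visit in period 1 and for the integrated study periods will be presented". For shifts, in the next sentence: "Weight shifts from reference to each visit by treatment group will be presented, where the reference is the screening measurement". That sentence ends by naming four classes, the last being 10% or more: "using the following limits: ‘<0’, ‘(0-7%]’, ‘(7-10%]’ and ‘≥10".

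The general sections of the SAP determine how an integrated table is built:

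- **4.1:** "summary tables by treatment groups will have 2 versions", one for Period 1 and one for the integrated periods, unless otherwise specified. Section 8.1 likewise runs the safety analysis for both.
- **3.3:** "Patients that were randomized to Placebo in Period 1 will be counted according to the initial dose". The dose meant is the first TV-44749 dose given to them in Period 2.
- **4.2:** "For patients that were assigned to placebo group in Period 1, the baseline value is the baseline value for Period 2", that is, the last value before the week 8 injection. For patients first randomized to TV-44749 it is the last value before their first dose.
- **8.1:** "Data from Period 1 for placebo patients will not be included in the integrated summaries".
- **8.2:** a former-placebo patient's exposure is counted from visit 11 (week 8).

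The only provision for showing rollover patients apart is in 8.1: "for IDMC closed reviews, patients rolling over from Placebo group will be distinguished from patients who continued their active treatment assignment". It does not extend to the clinical study report.

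**The concern.** In integrated tables, everything else in the SAP starts a former-placebo patient's record at the first TV-44749 injection. The weight-shift table keeps screening as the reference for everyone. Such a patient's class then combines weight change during screening and eight weeks of placebo with change on drug, and reports the total under a TV-44749 dose. The percent-change table in the same section uses the 4.2 baseline, so the two weight tables can disagree for the same patient and visit.

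Protocol 2.3.1 notes that the olanzapine label warns of weight gain. Period 2 has no placebo group, so the integrated shares above 7% and 10% will be read as absolute figures with no control to subtract. Weight can move during the placebo phase for reasons unrelated to TV-44749: prior oral antipsychotics are tapered off before randomization (Protocol 4.1), and patients are hospitalized for at least four weeks with meals provided (Protocol 4.1 and 6.6.3). The error has no fixed direction, so it cannot be defended as conservative.

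**Working it through.** The SAP gives no figure that depends on this rule, so there is nothing to reproduce. The check is a comparison of definitions followed by arithmetic. Counts and durations come from the documents. All weight changes are assumed, because the documents give none.

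**1. Time from screening to first TV-44749 dose.** Screening lasts up to 8 days (10 if extended) and Period 1 lasts 56 days.
- Former-placebo patients: 8 + 56 = 64 days, or 10 + 56 = 66.
- Patients first randomized to TV-44749: 8 days, or 10.

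**2. How many patients.** SAP 2.5 plans about 640 randomized and 440 completing week 8, allocated 1:1:1:1.
- Placebo completers: 440/4 = 110. Re-randomized 1:1:1: 110/3 = 36.7 per dose.
- Share of a week 12 row: 36.7/(110 + 36.7) = 25.0%. This assumes equal attrition across arms, that all placebo completers enter Period 2, and rows aligned on calendar week.
- Share of all patients in an integrated column: 36.7/(640/4 + 36.7) = 36.7/196.7 = 18.6%.

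**3. Single patients.** Change from screening = (1 + placebo change) × (1 + on-drug change) − 1.

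| Screening, week 8, week 12 (kg) | From screening (8.7) | From first TV-44749 dose (4.2) |
|---|---|---|
| 80.0, 84.0, 86.0 | 86/80 − 1 = +7.5%, class (7-10%] | 86/84 − 1 = +2.4%, class (0-7%] |
| 80.0, 76.0, 82.0 | 82/80 − 1 = +2.5%, class (0-7%] | 82/76 − 1 = +7.9%, class (7-10%] |

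Equivalently, the on-drug gain needed to reach +7% from screening is 1.07/(1 + placebo change) − 1. It is 10.3% after a 3% loss on placebo and 3.9% after a 3% gain.

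**4. Share above 7% among former-placebo patients.** This is a simulation with assumed normal changes, independent between phases and compounded as in step 3. The placebo-phase mean runs from −2% to +2% and its SD from 2% to 4%. The row shift is 25% of the difference from the on-drug share.

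| On-drug change, mean (SD) | True share >7% on drug | Shown, lowest to highest | Shown at placebo mean 0, SD 3 | Row shift, range | Row shift, placebo mean 0, SD 3 |
|---|---|---|---|---|---|
| 2% (3%) | 4.8% | 2.6% to 27.8% | 12.2% | −0.5 to +5.8 points | +1.9 points |
| 4% (6%) | 30.9% | 20.7% to 44.5% | 32.5% | −2.5 to +3.4 points | +0.4 points |

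Across these settings the above-7% status differs between the two references for 4.1% to 25.2% of former-placebo patients, about 1.5 to 9 of 37 per dose.

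**5. Class limits.** The first class is strictly below 0 and the second excludes 0, so no change has no class. The third includes 10% and the fourth starts at 10%, so exactly 10% falls in both. With an assumed mean weight of 80 kg (SD 12), mean change of 0 or 2% and SD of 2-3%, the share with a recorded change of exactly zero depends on recording precision:
- 0.1 kg: 1.4-2.6%, about 2-3 of 110 patients.
- 0.5 kg: 6.8-12.6%, about 7-14 of 110.
- 1 kg: 13.4-24.5%, about 15-27 of 110.

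The documents do not state the precision.

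**The case against.** The strongest reply is that the affected table is inferred. In 8.7 the percent-change and BMI sentences both name the integrated periods, and the shift sentence between them does not. If the shift table is for Period 1 only, the reference problem disappears, because placebo patients are shown there as placebo. This stands as a condition. But nothing in 8.7 restricts the table to Period 1, and the defaults in 4.1 and 8.1 produce both versions.

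A second reply is that 4.2 and 8.1 would govern any integrated version, so former-placebo patients would be measured from week 8 in practice. The explicit word *screening* in 8.7 cannot be read as the 4.2 baseline, so a programmer following the text would use screening.

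Third, screening may have been chosen because it precedes the oral olanzapine tolerability doses and, for patients admitted at study entry, most of the inpatient stay. That is a fair reason for patients first randomized to TV-44749, who are the majority of every column. It does not justify carrying eight placebo weeks into a drug column.

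Fourth, the sizes rest on assumptions, and the extremes need a placebo mean of ±2%. This stands. The central cases move the row by only +1.9 and +0.4 points. If weight lost on placebo tends to be regained, the effect shrinks further: with a correlation of −0.5 between phases in the mean 0, SD 3 case against an on-drug 2% (3%), the share above 7% is about 5%, close to the true 4.8%. The 25% weight is also an upper figure, since entry to Period 2 requires clinical stability. Individual misclassification remains in all these cases.

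Finally, Period 2 stays uncontrolled whichever reference is used, and calendar-week rows would mix exposure durations. Both are true, and the change proposed here does not claim to cure either.

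**Conclusion.** The concern holds, at minor severity. Followed as written, SAP 8.7 reports up to 64 days (66 with extended screening) of pre-drug weight change under a TV-44749 dose for about 37 patients per dose, against the baseline rule that the SAP applies elsewhere in integrated tables. The plausible effect on an arm's share above 7% runs from a few tenths of a point to several points, in either direction. That size is illustrative: it rests on assumed weight changes, independent phases, calendar-week rows and full rollover of placebo completers.

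The conclusion depends on an integrated shift table being produced. The Period 1 contrast between arms is unaffected in expectation, and the contrast between doses is little affected because rollover patients are split 1:1:1. No efficacy analysis is involved, and all weights are listed. The faulty class limits are a separate, smaller error that applies to both versions of the table.

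**What to change.** In SAP 8.7, state that the integrated weight-shift table uses the SAP 4.2 integrated baseline: the last weight before the first TV-44749 dose, which is visit 2 for patients first randomized to TV-44749 and pre-dose visit 11 for former-placebo patients. Change the classes to ≤0, (0-7%], (7-10%] and >10%. If the table is meant for Period 1 only, say so; the limits still need correcting.

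The cost is one clause and two limits. No new data are needed: weight belongs to the visit 11 physical examination, which is done before re-randomization (Protocol 6.9.1 and Appendix B). One downside should be accepted knowingly: a patient who loses weight on placebo and regains it will count as gaining on TV-44749. The placebo-phase change remains visible in the Period 1 table.
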